#### 8.6.3 Missed Doses

Missed doses may be made up as long as they are not taken within 24 hours of the next scheduled dose.

### 8.7 Study Drug Accountability

Study drug (azithromycin or placebo and open-label azithromycin) dispensed to subjects will be counted as noted in the Schedule of Events. Study drug distribution will be recorded, including study drug identifier (randomized period), date, quantity, and subject ID.

### 8.8 Measures of Treatment Compliance

Subject daily diaries recording study drug and TISP use will be reviewed and the number of doses taken will be recorded throughout the study. Subjects will be asked to bring study drug bottles and the diary to each study visit and the number of study drug capsules remaining will be compared with the number ideally taken. Subjects will be questioned at each visit about missed or extra doses of study drug, open-label azithromycin, and/or TISP. Treatment compliance for

study drug will be based on the number of doses reported taken by the subject, with consideration of drug returns.

## 8.9 Standard of Care Treatment with TISP

Subjects will not be allowed to change from inhaled tobramycin solution to inhaled tobramycin powder (i.e., TOBI® Podhaler) or vice versa while enrolled in the study. Either tobramycin delivery mechanism will be allowed but subjects must be stable on one delivery mechanism, either solution or dry powder, for one or more on/off cycles (i.e., 8 weeks) prior to Visit 1.

### 8.9.1 Administration Instructions

If the subject is using inhaled tobramycin solution, inhaled tobramycin will be administered as per the manufacturer's instructions (e.g., 300 mg in 4 or 5 mL solution, nebulized and inhaled twice daily using a device approved by the drug manufacturer). Tobramycin solution should be nebulized with an approved nebulizer and air compressor without mixing or diluting with other solutions, according to manufacturer instructions.

If the subject is using inhaled tobramycin powder, the TOBI Podhaler will be administered as per the manufacturer's instructions (e.g., 4 dry powder capsules inhaled twice daily using the supplied device).

Ideally, tobramycin should be inhaled twice daily following airway clearance. Airway clearance includes any inhaled bronchodilators, mucolytics (e.g., DNase, hypertonic saline), and mechanical clearance devices (e.g., Vest, acapella, hand percussion). If airway clearance is not clinically recommended at least twice daily, then tobramycin should be inhaled following the single airway clearance session and again each day without airway clearance.

Tobramycin should be stored refrigerated per manufacturer's instructions.

## 9 STUDY PROCEDURES AND GUIDELINES

The procedures described below will be performed at the visits noted in the Schedule of Events (Appendix 1) and in Section 10.

Prior to conducting any study-related activities, written informed consent and the Health Insurance Portability and Accountability Act (HIPAA) authorization must be signed and dated by the subject or subject's legal representative. If appropriate, assent must also be obtained prior to conducting any study-related activities.

### 9.1 Clinical Assessments

#### 9.1.1 Concomitant Medications

All concomitant medication and concurrent therapies will be documented as noted in the Schedule of Events. Dose, route, unit, frequency of administration, indication for administration and dates of medication will be captured.

#### 9.1.2 Demographics and CFF Registry ID

Demographic information (date of birth, sex, race) will be recorded at Visit1. CF Registry ID number will be recorded for participating CF subjects who provide optional consent.

### 9.1.3 Medical History

Relevant medical history, including history of current disease, other pertinent respiratory history, and information regarding underlying diseases will be recorded. Previous use of azithromycin and inhaled tobramycin will also be collected.

### 9.1.4 CF Diagnosis

Diagnosis date and sweat chloride test, CF genotype, and transepithelial nasal potential difference test result will be recorded as available.

### 9.1.5 Physical Examination

A complete or abbreviated physical examination will be performed by a licensed professional (MD, NP, RN, PA) as noted in the Schedule of Events. The abbreviated exam includes respiratory, cardiovascular, and abdominal assessments.

After the initial exam at Visit 1, new clinically significant, abnormal physical exam findings must be documented as AEs.

### 9.1.6 Weight and Height

Weight will be measured on the same scale and recorded as noted in the Schedule of Events. Adults and children may remain in clothes (without shoes). A standing height will be measured and recorded as noted in the Schedule of Events.

Note that accurate height measurements will significantly improve the data quality, as this is incorporated into equations used to derive the FEV1% of predicted based on a reference population.

### 9.1.7 Vital Signs

Resting (minimum of 5 minutes) measurements of body temperature, blood pressure, pulse and respirations will be performed and recorded as noted in the Schedule of Events.

### 9.1.8 Spirometry

Spirometry will be performed at as noted in the Schedule of Events and in accordance with the current American Thoracic Society recommendations for the performance and interpretation of tests.

Subjects should be encouraged to perform the same airway clearance routine and inhaled bronchodilators prior to each study visit. Additional instructions for study personnel will be provided in the Study Manual.

### 9.1.9 Respiratory Culture

If the patient does not have sufficient culture history to assess eligibility, a respiratory culture may be collected prior to randomization. If the respiratory culture is positive, the remaining Visit 1 procedures and randomization will be conducted at a subsequent visit.

**9.1.10 Subject Questionnaire: CFRSD-CRISS**

The subjects will be given a CF specific symptom diary called the CFRSD-CRISS as noted in the Schedule of Events. This diary includes 8 questions and takes less than 5 minutes to complete. The CFRSD-CRISS should be administered at the beginning of each visit.

**9.1.11 Subject Questionnaire: Cystic Fibrosis Questionnaire-Revised (CFQ-R)**

The CFQ-R is a patient reported quality of life instrument, regarding symptoms and mood over the preceding 2 weeks. The age appropriate version of the CFQ-R will be completed at the beginning of each visit as noted in the Schedule of Events by the subject. Completion should take less than 5 minutes.

**9.1.12 Subject Diary**

Subjects will be requested to complete a daily diary to document daily dose of study drug treatments and TISP treatments, and to record changes in concomitant medications and symptoms through the end of the study. The diary will be dispensed and reviewed as noted in the Schedule of Events.

**9.1.13 Electrocardiogram (ECG)**

Standard 12-lead ECG tracing will be obtained as noted in the Schedule of Events. ECG is only needed for an acute visit if the subject has a cardiovascular-related AE or will no longer be participating in the study.

Testing will be conducted and reviewed at the site by trained personnel with experience interpreting electrocardiograms. Any test results of clinical concern, should be reported to the Medical Monitor to determine follow up actions as described below.

Testing will be performed using an ECG machine that automatically calculates the heart rate and measures PR, QRS, QT, and QTc intervals. All tests will be measured in Lead II.

Abnormal results at the time of follow-up testing are defined as a QTc >500 msec, or an increase in QTc of  $\geq 60$  msec. It is recommended that testing be repeated after 10 minutes for any ECGs that meet the protocol definition for abnormal. If test results are confirmed, subjects will be instructed to stop study drug or open-label azithromycin and the site investigator will continue to observe the subject for clinical signs of arrhythmia (specifically torsades de pointes).

The ECG tracing will be collected for additional safety review.

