## 1 BACKGROUND

Projected median survival of those with cystic fibrosis (CF) has dramatically improved in recent decades, largely as a result of new medications and therapies. *Pseudomonas aeruginosa* (*Pa*) is the most common pathogen in the airways of people with CF. By early adolescence, half of all patients with CF are chronically infected with *Pa*. This prevalence increases to 70% or more by early adulthood, and persistent *Pa* airway infection is linked to more rapid loss of lung function and earlier mortality. Inhaled antibiotics achieve high airway concentrations while avoiding many safety concerns associated with prolonged systemic drug exposure. Strategies to eradicate initial *Pa* airway infection or treat chronic infection have proven beneficial.

The aminoglycoside tobramycin was the first inhaled anti-pseudomonal antibiotic commercially developed for CF and remains the most prescribed inhaled antibiotic used in the US. Roughly two thirds of all US patients with CF and chronic *Pa* are prescribed inhaled tobramycin—typically as 28 days of on-off cycles. Long-term use of oral azithromycin has also been shown to improve lung function and reduce exacerbations in CF patients with chronic *Pa* airway infection. While the mechanism of action is uncertain and potentially multifactorial, azithromycin has immunomodulatory effects and may function as an anti-inflammatory agent in CF. Azithromycin is widely prescribed and is now the most common chronic antibiotic used in CF patients with persistent *Pa*. In queries of recent clinical trials and the US CF Foundation National Patient Registry, we find that ~70% of all patients with *Pa* and 75% of those prescribed inhaled tobramycin are now also prescribed oral azithromycin on a chronic basis.

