## 2.1 Risk / Benefit Assessment

No experimental or new medications are being introduced to subjects during this study. Removal of chronic azithromycin may decrease lung function or increase the rate of pulmonary exacerbation, based on prior studies of azithromycin in similar patients. Our preliminary data does not support this concern and suggest that removing azithromycin may be protective in the majority of subjects also using inhaled tobramycin. This includes better clinical outcomes in lung function (FEV1), patient reported quality of life, and time to need additional antibiotics. However, a withdrawal study of either medication has never been reported and our preliminary data on lung function may not fully predict the risk of pulmonary exacerbation. Subjects experiencing a pulmonary exacerbation will be treated but will not be removed from the study.

Identifying an undesirable drug-drug interaction pertinent to over 50% of US patients with CF has clear and important safety and efficacy implications. Given that both of these medications benefit from strong support in US consensus guidelines, answering this question is a high priority.

Recent reports raise concern about potential proarrhythmic cardiotoxicity with oral azithromycin treatment in non-CF populations. Patients with CF account for a significant portion of chronic azithromycin use in the US and cardiac arrhythmias have not been linked to this therapy. Similarly, the relative risk of cardiovascular death attributable to azithromycin was reported as <1 per 100,000 antibiotic courses in low risk patients. There are approximately 30,000 CF patients in the entire US, and a repeat study found no increased risk in younger, lower risk adult populations. However, this study provides an opportunity to analyze electrocardiograms (ECGs), focusing on any effect on QTc interval, in a group of CF subjects both on and off of azithromycin.

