### 5.2 Secondary Endpoints

#### Randomized Period

Secondary Endpoints:

- Difference between the azithromycin and placebo treatment groups in the relative change in FEV1(liters) during administration of TISP from Visit 2 to Visit 3.
- Difference between the azithromycin and placebo treatment groups in the change from Visit 1 to Visit 3 in the Cystic Fibrosis Respiratory Symptom Diary (CFRSD) - Chronic Respiratory Infection Symptom Score (CRISS®)
- Difference between the azithromycin and placebo treatment groups in the change from Visit 1 to Visit 3 in the scales derived from the CFQ-R

Exploratory Secondary Endpoints:

- Difference in adverse event rates and rates of abnormal QTc parameters from Visit 1 through Visit 3 between the azithromycin and placebo treatment groups
- Difference in the proportion of subjects hospitalized from Visit 1 through Visit 3 between the azithromycin and placebo treatment groups
- Difference in the proportion of subjects

prescribed acute oral, inhaled and IV antibiotics from Visit 1 through Visit 3 between the azithromycin and placebo treatment groups

- Difference in the proportion of subjects experiencing a protocol-defined pulmonary exacerbation requiring antibiotic therapy from Visit 1 through Visit 3 between the azithromycin and placebo treatment groups
- Difference between the azithromycin and placebo treatment groups in the absolute change from Visit 1 to Visit 3 and Visit 2 to Visit 3 in FEV1 (liters and % predicted), absolute and relative change in FVC (liters and % predicted), and absolute and relative change in FEF25-75%
- Difference between the azithromycin and placebo treatment groups in the change from Visit 1 to Visit 3 in weight
- Difference in the change from Visit 1 to Visit 3 in sputum *Pa* bacterial density between the azithromycin and placebo treatment groups

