2.5 Definitions

Baseline – Baseline refers to Visit 1 (Day -14) when participants were randomized.

Study drug – During the randomized period, the study drug refers to the drug the participant was randomized to (either azithromycin or placebo). During the open-label period, the study drug refers to open-label azithromycin.

Treatment group – During the randomized period, the treatment group refers to participants randomized to either azithromycin or placebo. During the open-label period, the treatment group refers to participants either remaining on azithromycin or switching from placebo to azithromycin.

References

1. Emerson, SS and Fleming, TR. Symmetric group sequential test designs. *Biometrics*. 45:905-923, 1989.

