The incidence of AEs (including emergent abnormal QTc parameters) between the azithromycin and placebo treatment groups is tabulated by seriousness, severity, and relationship to study drug. The proportion of participants with at least one (S)AE, the average number of (S)AEs per patient, and the rate of (S)AEs per day of follow-up are reported. Poisson regression modeling is used to derive rate ratios and corresponding 95% confidence and to compare groups using a two-sided 0.05 level test. The difference in the proportion of participants experiencing at least one (S)AE between treatment groups is also reported, with corresponding 95% confidence intervals calculated using the Newcombe-Wilson method and p-values derived from a Fisher's exact test. Histograms showing the frequency of the number of (S)AEs in each treatment group are included.

All reported SAEs and AEs are coded using MedDRA and grouped by body system. Detailed summary tables of individual (S)AEs grouped by SOC are included to show the number and percent of participants experiencing each (S)AE by treatment group. The number and rate of events for each (S)AE is also reported by treatment group. Poisson regression is used to derive rate ratios and corresponding 95% confidence intervals comparing treatment arms for each SOC. Treatment groups are compared by the proportion of participants experiencing (S)AEs by System Organ Class (SOC) as well as the difference in proportions with corresponding 95% confidence intervals to compare treatment arms.

All SAE narratives are included in a listing appended to this report.

A.5 Summary of Spirometry Results

The primary endpoint is the difference between the azithromycin and placebo treatment groups in the relative change from Visit 1 to Visit 3 in FEV1 (liters). The primary efficacy analysis is conducted on the m-ITT population and repeated on per-protocol population. Predicted values for spirometry measures at each visit are calculated using the Global Lung Initiative reference equations.

A linear regression model adjusted for randomization strata is used to compare the primary endpoint between treatment groups. Least squares means and the treatment effect are presented

along with corresponding 95% confidence intervals and p-values. The primary analysis is adjusted for the group sequential monitoring.

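### The only planned QTc analysis counts abnormal results against high, one-directional thresholds and is very unlikely to show a modest azithromycin effect; add an exploratory comparison of mean QTc change

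*Protocol*

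**What the plan says.** Protocol 2.1 notes reports of proarrhythmic risk with azithromycin in non-CF populations. It then says the study offers an opportunity to analyse ECGs, "focusing on any effect on QTc interval, in a group of CF subjects both on and off of azithromycin".

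The matching endpoint in Protocol 5.2 is exploratory: "Difference in adverse event rates and rates of abnormal QTc parameters from Visit 1 through Visit 3 between the azithromycin and placebo treatment groups". Protocol 9.1.13 supplies the definition: "Abnormal results at the time of follow-up testing are defined as a QTc >500 msec, or an increase in QTc of" 60 msec or more. It does not name the ECG from which the increase is measured. SAP 2.5 states "Baseline refers to Visit 1 (Day -14) when participants were randomized", and Visit 1 is the only scheduled ECG before Visit 3.

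For analysis, SAP A.4 says "The incidence of AEs (including emergent abnormal QTc parameters) between the azithromycin and placebo treatment groups is tabulated by seriousness, severity", with causality as a third heading; Protocol 15.4 says the same. The continuous endpoints that Protocol 15.4 models like the primary endpoint are sputum density, weight, patient-reported scales and spirometry. QTc is not among them, and SAP A.5 to A.8 contain no QTc analysis.

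Inclusion criterion 11 admits current users and people with past chronic use, and does not require current use. The Visit 1 ECG comes before randomization and dispensing, and the placebo-arm washout starts after it (Protocol 4.1 and 10.1). Protocol 1 reports that "75% of those prescribed inhaled tobramycin are now also prescribed oral azithromycin on a chronic basis". Randomization is stratified by azithromycin use in the past 30 days (Protocol 8.1).

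**The concern.** The stated interest is any QTc effect, but the planned analysis is a count of extreme results. A mean shift of 5-15 msec would move very few people past 500 msec or through a 60 msec rise.

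The entry rules reduce the count's sensitivity further. There are four paths from Visit 1 to Visit 3:

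- **User assigned azithromycin:** no drug-induced change is expected.
- **User assigned placebo:** any drug effect appears as a fall, which the change criterion does not count.
- **Non-user assigned azithromycin:** any drug effect appears as a rise. This is the only path on which the change criterion can register the drug.
- **Non-user assigned placebo:** no drug-induced change is expected.

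At stake is the interpretation of a near-empty table. Few or no events would be expected with or without a modest effect, so the table would say little about the safety question that the protocol raises. The same ECGs could estimate the effect in msec.

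**Working it through.** **Inputs from the documents.** About 120 randomized 1:1, with 110 evaluable (55 per arm). Tests are two-sided at 0.05. The thresholds are as above. Azithromycin use is 75% in the source population; the enrolled share is unknown.

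**Assumed, not in the documents.** SD of QTc change (s) 15, 20 or 25 msec; true effect (e) 5, 10 or 15 msec; share on azithromycin at Visit 1 (f) 60%, 75% or 90%; normally distributed changes.

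**The plan's own figure.** The documents give no QTc power. The FEV1 power (7.5%, SD 13, 55 per arm) is stated as 85%. A t-test with standard error 13 × √(2/55) gives 85.0%, so it reproduces. It is used here only to fix the 55 per arm.

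**Who can show what, at f = 75%.** 0.75 × 120 = 90 participants would have an on-drug Visit 1 ECG, 45 per arm. That leaves 15 non-users per arm (24 at 60%, 6 at 90%).

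**Expected rises of 60 msec or more.** Let T(x) be the upper normal tail.

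- Azithromycin arm: p = f·T(60/s) + (1−f)·T((60−e)/s)
- Placebo arm: p = f·T((60+e)/s) + (1−f)·T(60/s)

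For e = 10, s = 20 and f = 0.75:

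- Azithromycin: 0.75 × 0.00135 + 0.25 × 0.00621 = 0.00256; × 55 = 0.14 events.
- Placebo: 0.75 × 0.00023 + 0.25 × 0.00135 = 0.00051; × 55 = 0.03 events.

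The largest case at 75% use (e = 15, s = 25) gives 0.83 v 0.17 events. At 60% use the same case gives 1.06 v 0.23, and at 90% use 0.60 v 0.11.

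**What a difference would need.** With 55 per arm, Fisher's exact test (used in SAP A.4 for the proportion with an event) gives p = 0.057 for 5 v 0 and p = 0.027 for 6 v 0. Its power is below 0.1% in every scenario with 60-90% use.

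**Which cause is larger.** Set f = 0, so that nobody is on azithromycin at Visit 1. Power is still at most 0.9% (e = 15, s = 25; 1.98 v 0.45 events). The threshold does most of the damage and the on-drug baseline adds to it.

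**The limb above 500 msec.** This limb is absolute and needs no baseline. Assuming an off-drug mean of 415 msec and a between-person SD of 20-25 msec, expected events per 55 are at most 0.14 v 0.02.

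**Mean change on the same ECGs.** The arm means are (1−f)·e for azithromycin and −f·e for placebo. Their difference is e for any f, so withdrawal and starting contribute with the same sign. The 95% CI half-width is 1.982 × s × √(2/55).

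| SD (msec) | CI half-width (msec) | Power, 5 msec | Power, 10 msec |
|---|---|---|---|
| 15 | 5.7 | 41% | 93% |
| 20 | 7.6 | 26% | 74% |
| 25 | 9.4 | 18% | 55% |

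These are unadjusted t-test figures.

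**The case against.** The other side has several fair points.

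- **Purpose.** Protocol 2.1 speaks of an opportunity, not an objective. The endpoint is exploratory and the thresholds also serve as a participant-safety rule. Tabulating outliers is a legitimate safety summary. This stands, and it is why the definition should stay and the addition should be exploratory.
- **Validity of the contrast.** A reader might infer that on-drug Visit 1 ECGs make the endpoint unable to show an on/off effect. The documents do not support that. Visit 3 is a randomized comparison, allocation is balanced on recent azithromycin use, the 500 msec limb needs no baseline, and non-users who start azithromycin can register a rise. The weakness is low sensitivity, not bias.
- **Baseline use.** A reader might also infer that most enrolled participants will be users. The 75% describes patients prescribed inhaled tobramycin; there is no enrolment quota, and current use is not required.
- **Completeness of the SAP.** The SAP refers to table shells and further appendices that are not in the supplied text. The absence of a msec analysis is therefore established only for that text.
- **Outside inputs.** The QTc SD and effect are assumptions, and nothing in the documents says that an empty table would be presented as no effect. Both points stand. Across the assumed range, however, the count is never informative.
- **Limits of the alternative.** Mean change has low power for 5 msec. That is true, but its interval still bounds the effect.

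**Conclusion.** The point holds as a matter of sensitivity. The planned QTc count is a poor tool for the modest on/off effect that Protocol 2.1 says could be examined, and the supplied text plans nothing better. At 75% baseline use the expected number of rises of 60 msec or more runs from near zero to 0.83 in the azithromycin arm of 55, and is at most 0.31 under placebo. About one event is the most expected at 60% use. Six against none would be needed for significance. The high thresholds are the main cause; the on-drug baselines are secondary.

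The event counts rest on the assumed SDs, effects, user share and normality. Two conclusions do not depend on the user share: the threshold count has almost no power, and the mean-change contrast recovers the full effect. The abnormal-QTc rule is not at fault as a safety rule. This is an inexpensive improvement to an exploratory analysis and does not affect the primary result.

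**What to change.** Leave the abnormal-QTc definition, the safety rule and the tabulation as they are. Add to Protocol 15.4 and SAP A.4:

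1. An exploratory between-arm comparison of QTc change in msec from Visit 1 to Visit 3, by the existing strata-adjusted linear regression with Visit 1 QTc as a covariate, reported as an estimate with 95% CI.
2. The same change shown descriptively by the existing stratum of azithromycin use in the past 30 days.
3. A statement that Visit 1 is the reference ECG for the change.
4. One correction formula where QT and heart rate are available, and the machine-calculated QTc otherwise.
5. A statement that few or no threshold events will not be interpreted as evidence of no QTc effect.

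The cost is a short text change, one model and one table. No new ECG is needed. The documents do not show that QT, heart rate or QTc are entered in the database, so values may have to be abstracted from the collected tracings across about 40 sites. The non-user subgroups will be small, about 15 per arm at 75% use, so the stratum display should stay descriptive.
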